6.2 Premature Discontinuation

Subjects who discontinue participation in the study prematurely (i.e. prior to Visit 12) will complete an end-of-study visit including all procedures listed for Visit 12.

A subject will be withdrawn from the study under any of the following circumstances:

- Subject's request at any time for any reason.
- Physician's determination that subject's further participation in the protocol is not in the subject's best interest.
- The Sponsor's decision.
- Health Authorities' decision.

For any discontinuation, the Investigator will obtain all the required details and document the date of and the reason for the discontinuation in the case report form (CRF). If possible, Week 48 ETDRS visual acuity should be obtained.

If the reason for withdrawing from the study is an AE, the specific event will be recorded in the CRF.

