## Responder

### Eye Responder

#### Definition 1

Responder at week 48 and also at week 96, will be defined by an improvement of at least 15 letters in the ETDRS score compared to baseline, *or* being greater than a Snellen acuity equivalent of 20/200. Early discontinuations (prior to W48 for the primary endpoint) will be considered as non responder. For week 96 two analyses will be performed: One for completers and one for subjects who don't have the Week 96 value available. If the week 96 ETDRS score is not available, then the previous visit value will be used.

#### Definition 2

Responder, at week 48 and also at week 96, will be defined by having an ETDRS Score equal to or greater than 20 letters. Early discontinuations (prior to W48 for the primary endpoint) will be considered as non responder. For week 96 two analyses will be performed: One for completers and one for subjects who don't have the Week 96 value available. If the week 96 visual acuity score is not available, then the previous visit value will be used.

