## Subject Responder

Responder, at week 48 and also at week 96, will be defined as a subject whose ETDRS score of the treated eye is at least 15 letters better than the sham eye *or* whose treated eye has a LogMAR acuity of at least 0.3 LogMAR better than the sham eye. Early discontinuations (prior to W48 for the primary endpoint) will be considered as non responder. For week 96 two analyses will be performed: One for completers and one for subjects who don't have the Week 96 value available. If the week 96 visual acuity score is not available, then the previous visit value will be used.

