### Eye responders

The responder analyses at both Week 48 and Week 96 will be based on a McNemar test comparing all-GS010 eyes against all-Sham eyes.

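### The SAP's responder rule sets aside Week 48 acuity measured after withdrawal, acts as deletion in the McNemar test, and leaves Week 96 status unclear

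*SAP*

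**What the plan says.** SAP 5.4 gives two eye-responder definitions and one subject-responder definition. Each covers both time points; Definition 1 begins "Responder at week 48 and also at week 96, will be defined by an improvement of at least 15 letters in the ETDRS score". All three carry the same sentence on withdrawals: "Early discontinuations (prior to W48 for the primary endpoint) will be considered as non responder". No exception is written for a subject who has a Week 48 value.

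Protocol section 6.2 deals with the same subjects. Those who leave early "will complete an end-of-study visit including all procedures listed for Visit 12", which include ETDRS acuity. It adds: "If possible, Week 48 ETDRS visual acuity should be obtained".

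For Week 96, Definition 1 says "If the week 96 ETDRS score is not available, then the previous visit value will be used", and the other two definitions say the same of the visual acuity score. All three definitions also contain: "For week 96 two analyses will be performed: One for completers and one for subjects who don't have the Week 96 value available".

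SAP 9.5.5 sets the eye-level test: "The responder analyses at both Week 48 and Week 96 will be based on a McNemar test comparing all-GS010 eyes against all-Sham eyes". Subject responders are analysed differently, with a randomization test against an expected rate. SAP 9.5.3 gives all of alpha to the primary endpoint and calls everything else supportive.

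**The concern.** Treatment is a single injection on Day 0, so discontinuation means leaving the study, not stopping a drug. An acuity measured at Week 48 in someone who has formally left is still a valid Week 48 outcome of that injection. The protocol asks for it, yet the responder rule gives it no effect. The primary analysis does the opposite, because SAP 5.5.1 imputes only when Week 48 data are missing.

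Counting drop-outs as failures is usually defended as conservative. That defence relies on independent arms. Here each subject supplies one GS010 eye and one sham eye, both eyes leave together, and the test is paired.

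At stake is a named secondary endpoint at two time points. It may ignore observed outcomes, and it may show a change in responders between Week 48 and Week 96 that comes only from the coding.

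**Working it through.** **Plan's own figure.** The documents give no size, power or drop-out figure for the responder analysis. The planned N is used below. It reproduces from the SAP 3.3 inputs for the primary endpoint (standardized difference 0.50, two-sided alpha 0.05, power 85%): ((1.960 + 1.036)/0.50)² = 35.9, rounded up to 36. It has no further bearing on this point.

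**Step 1: observed value against the rule.** Take a subject who leaves after Week 24 and is measured at Week 48, with the GS010 eye a responder and the sham eye not. Write status as (GS010, sham).
- Measured status: (1,0).
- Status under the SAP 5.4 sentence: (0,0).
- Primary LogMAR analysis: uses the measured values, since nothing is missing.

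**Step 2: effect on McNemar.** Let b be the pairs where only the GS010 eye responds and c the pairs where only the sham eye responds. The exact test refers b to a binomial(b + c, 1/2); the asymptotic statistic is (b − c)²/(b + c). A (0,0) pair adds nothing to b or c, so p is the same as with the subject deleted. The rates do change: the subject stays in the denominator, so both rates and their difference shrink.

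**Step 3: illustration (counts assumed).** Start from b = 10, c = 2. Add two early drop-outs, each with an observable status. Under the SAP rule every row is reported as 10 v 2.

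| True status of the two drop-outs | b v c | Exact two-sided p |
|---|---|---|
| both (0,0), or coded so | 10 v 2 | 158/4096 = 0.039 |
| both favour sham | 10 v 4 | 2942/16384 = 0.18 |
| one favours sham, one concordant | 10 v 3 | 756/8192 = 0.092 |
| one each way | 11 v 3 | 940/16384 = 0.057 |
| one favours GS010, one concordant | 11 v 2 | 184/8192 = 0.022 |
| both favour GS010 | 12 v 2 | 212/16384 = 0.013 |

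The SAP does not say whether the test is exact or asymptotic. Asymptotic p is 0.021 for 10 v 2, 0.109 for 10 v 4 and 0.0075 for 12 v 2.

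**Step 4: power and dilution (rates assumed).** Let P(GS010 only) = 0.30, P(sham only) = 0.05, N = 36, with drop-outs following the same rates.

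| Drop-outs coded (0,0) | Exact power | Rate difference |
|---|---|---|
| 0 | 67.9% | 0.250 |
| 2 | 64.6% | 0.25 × 34/36 = 0.236 |
| 4 | 60.9% | 0.25 × 32/36 = 0.222 |
| 6 | 57.0% | 0.25 × 30/36 = 0.208 |
| 8 | 52.8% | 0.25 × 28/36 = 0.194 |

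With 0.25/0.03, power falls from 66.1% to 53.8% at six drop-outs; with 0.35/0.10, from 54.8% to 44.6%. These losses are upper limits, since only drop-outs actually measured at Week 48 can be recovered.

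**Step 5: Week 96.** The parenthesis in the rule can be read in two ways.
- *Rule limited to Week 48.* The carry-forward sentence governs Week 96. The Step 1 subject is (0,0) at Week 48. If the previous visit means the last one attended, the subject becomes (1,0) at Week 96 on Week 24 data. If it means the scheduled Week 72 visit, there is no value and the text assigns no status.
- *Rule covers both weeks.* One sentence makes the subject a non-responder at Week 96, while the other takes status from an earlier visit. They contradict each other.

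The reference to the primary endpoint does not settle this, because the primary endpoint is LogMAR change, not response. Read literally, the second Week 96 analysis also contains only subjects without a Week 96 value.

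**The case against.** The strongest reply is that this may affect nobody. Protocol 6.2 asks for the measurement only if it can be had, no drop-out rate is given, and the counts above are assumed. The endpoint is supportive with no alpha, and the LogMAR primary is untouched. All of that stands and limits the weight of the point, but it does not make the wording right.

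The Week 96 objection also stands in part. The parenthesis can fairly be read as confining the rule to Week 48, so a reader who infers a flat contradiction goes further than the text. The second Week 96 analysis was very probably meant to include all subjects, with the carry-forward applied to those lacking a value.

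Four stronger inferences are tempting but unsupported:
- *The rule favours GS010.* Ties remove discordant pairs in either direction.
- *Two subjects could reverse the conclusion either way.* In the exact-test illustration, moving from 0.039 to 0.18 crosses 0.05; moving to 0.013 does not.
- *The rule conceals withdrawal that differs between eyes.* Withdrawal is a subject-level event; only outcomes differ by eye.
- *The tie argument covers Subject Responder.* That status is one value per subject under a different test, so a drop-out there counts as a failure.

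**Conclusion.** The point holds on the text in three parts. First, the trigger is discontinuation, so acuity measured at Week 48 after withdrawal is ignored in all three responder definitions; this rests on taking the sentence as written. Second, for the eye-level McNemar test the rule is equivalent to deletion as far as the p-value goes. That is exact and needs no assumption. The responder rates and their difference are diluted. Third, the Week 96 text needs reconciling on either reading, though which fault it contains depends on the reading.

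The size cannot be fixed from the documents. On assumed counts, two drop-outs among 36 subjects leave the reported exact p at 0.039 when the full data could give anything from 0.013 to 0.18. The wording should be corrected; the primary conclusion of the trial does not depend on it.

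**What to change.** In SAP 5.4, in all three definitions, replace the discontinuation sentence with:

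*Status at Week 48 (Week 96) is determined from the acuity measured at that time point whenever available, including after discontinuation; an off-chart measurement counts as available, not missing. Subjects with no measurement at that time point are non-responders.*

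The off-chart clause is needed because off-chart eyes have no ETDRS score and could otherwise be taken as missing.

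Then:
- Apply that one missing-value rule at both weeks. Remove the carry-forward sentence or confine it to a named sensitivity analysis, and define there what the previous visit is.
- Define the two Week 96 analyses as completers and all ITT subjects.
- For the eye-level McNemar test, add one sensitivity analysis for subjects with no measurement: the GS010 eye is a non-responder and the sham eye keeps its last observed status. This gives the adverse case that tie-coding cannot.
- For Subject Responder, only the observed-value and missing-value sentences apply, since status there is a between-eye comparison.

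The cost is SAP wording and one extra sensitivity run. Unmeasured subjects remain ties in the main McNemar test, which is why the sensitivity analysis is needed. The change must be made before the randomization code is broken for the Week 48 analysis, because protocol Appendix V allows no SAP amendment after that.

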## Subject Responder

Responder, at week 48 and also at week 96, will be defined as a subject whose ETDRS score of the treated eye is at least 15 letters better than the sham eye *or* whose treated eye has a LogMAR acuity of at least 0.3 LogMAR better than the sham eye. Early discontinuations (prior to W48 for the primary endpoint) will be considered as non responder. For week 96 two analyses will be performed: One for completers and one for subjects who don't have the Week 96 value available. If the week 96 visual acuity score is not available, then the previous visit value will be used.

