8.6 Method of Assigning Treatment

The right eye of each subject will be randomly allocated to receive either GS010 or sham treatment in a 1:1 allocation ratio. The fellow (left) eye will receive the treatment not allocated to the right eye. Therefore, each subject will receive GS010 in one eye and sham treatment in the fellow eye. Prior to randomization, each subject's better- and worse-seeing eye will be determined. Efron's minimization method will be used in the randomization process to balance as much as possible the two treatment groups (GS010 and sham) in the better-seeing eyes.

To enroll a subject (Visit 1), the Investigator will call an interactive response system (IRS) and provide brief details about the subject to be enrolled. Each subject will receive a subject number assigned at screening, which will serve as the subject identifier throughout the study. The subject number will be required in all communication between the Investigator (or designee) and the IRS regarding a particular subject. Subject numbers will be tracked via the IRS.

To randomize a subject (Visit 2), the masked Investigator (or designee) will call the IRS and provide brief details about the subject to be randomized. Eligible subjects will be randomized in a 1:1 ratio (right/left eye), taking into account the Efron's minimization method, using the IRS.

The IRS User Guide will describe the steps of the randomization process from the subject's screening up to before IVT injection.

An algorithm with a testing hierarchy will be employed prior to randomization to determine the better- and worse-seeing eye of each subject, as follows:

1. ETDRS visual acuity score for subjects able to read the ETDRS chart. The eye with the higher ETDRS score is the better-seeing eye. For subjects who cannot read the ETDRS chart ("off chart" subjects) a standard study procedure will be used to determine visual acuity based on counting fingers at a given distance. The eye with the best visual acuity based on this method is the better-seeing eye. If one eye of a subject is able to read letters on the ETDRS chart and one eye cannot, the eye able to read the ETDRS chart is the better-seeing eye.
2. SD-OCT parameters (to be used if there is no inter-eye difference based on Criterion 1):

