### 3. STUDY DESIGN

#### 3.1 OVERALL DESIGN

[figure not shown]
GS-LHON-CLIN-03B is a Phase III double-masked, sham-controlled, multicenter, multi-country study. Recruitment is competitive.

Both eyes will receive standard antiseptic preparation, administration of topical local ocular anesthetic agents and will undergo pupillary dilation. Administration of an intra-ocular pressure lowering agent will precede treatment. GS010 will be administered once during the study via a single intravitreal (IVT) injection. Sham IVT injection will be performed by applying pressure to the eye at the location of a typical procedure using the blunt end of a syringe without a needle.

The right eye of each subject will be randomly allocated to receive either GS010 or sham treatment in a 1:1 allocation ratio. The fellow (left) eye will receive the treatment not allocated to

the right eye. Therefore, each subject will receive GS010 in one eye and sham treatment in the fellow eye.

The schematic design of the study design is given below:

An algorithm with a testing hierarchy will be employed to determine the best- and worst-seeing eye of each subject prior to randomization. The randomization will be based on the right and left eye, because if the right eye is treated the left eye will receive sham and vice versa the treatment groups will be automatically balanced. However, the best- or worst-seeing eye at entry can be a confounding factor, and it cannot be discarded that the treatment effect will be the same in the best and worst seeing-eye. Secondarily, in order to verify this hypothesis with optimal power, an adaptive randomization technique called Efron's minimization ([Efron 1971](#)) method will be used to minimize the imbalance of treatment groups between the best-seeing eyes and worst-seeing eyes.

Masking will be accomplished with sham injection of the fellow eye. Thus treatment allocation will be double-masked for both the subject and the investigation (follow-up) team, except the physician and medical team that will perform the GS010 administration and sham injection and the first follow-up visit. Centralized analysis of the Early Treatment Diabetic Retinopathy Study (ETDRS) visual acuity results, automated visual fields, SD-OCT, color vision and contrast sensitivity will be performed.

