### 3.3 SAMPLE SIZE CONSIDERATIONS

Sample size calculation is based on the primary endpoint (LogMAR) and on the paired comparison of treated and sham eye. There is no published data regarding the within subject variance and the sample size calculation through paired comparison will therefore be very speculative for two reasons. The first reason is the within subject correlation between right and left eye and the second reason is the absence of information on the within and between subject variance of the LogMAR. Usually the within subject correlation is positive and the use of a null correlation is conservative. The absence of information on the LogMAR requires a second rough approximation of the mean and variance of LogMAR because the mean of ETDRS (Lam et al. 2014) is highly correlated to the variance of ETDRS ( $R^2 = 0.839$  for the log-log relationship). This correlation is in favor of the use of the LogMAR to stabilize the variance but the transformation from ETDRS mean and variance to LogMAR mean and variance requires additional assumptions. Starting with a mean 23.4 and a standard deviation of 28.3 (Lam et al.

2014) and a difference of 20 letters on average between treated and sham eye, using the relationship between the log mean and the log variance obtained with Lam et al. (2014) results (log variance = 1.743 log mean + 0.48,  $R^2 = 0.839$ ) and assuming a perfect lognormal distribution of ETDRS, the difference in means of the lognormal distributions is 0.65 (3.32 - 2.67) and the pooled standard deviation of the log distributions is 0.914. Assuming no correlation between both eyes, the within subject standard deviation is  $(2 \times 0.914^2)^{0.5} = 1.29$ . The standardized difference in means is therefore  $0.65/1.29 = 0.504$  rounded to 0.50. The sample size required to get a power of 85% is exactly 36 subjects.

In GS-LHON-CLIN-01(Phase I/II study), at week 48 the standard deviation (SD) for visual acuity of the between-eye difference in change from baseline was calculated as 0.594. Considering that in Phase III studies of GS010 detection of a 15 ETDRS letters or 0.3 LogMAR difference between treated and untreated eyes at outcome is a clinically reliable difference, the SD of the difference of 0.594 would provide a power/probability of 84% to detect such a difference based on the enrolment goal of 36 subjects each in the RESCUE and REVERSE Phase III clinical trials.

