### Responder Analysis

### Subject responders

The responder analyses at both Week 48 and Week 96 will be based on a randomization test comparing the observed rate of responders to the expected rate of responders under  $H_0$  (i.e. absence of treatment effect). Expected rate is defined as responder rate in the Sham group based on an improvement of at least 15 letters in the ETDRS score compared to baseline, or being greater than a Snellen acuity equivalent of 20/200.

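### Subject Responder is scored on the raw treated-versus-sham acuity gap with no baseline term, so a gap present before injection can count as a response and a real relative gain can be missed

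*SAP*

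**What the plan says.** SAP 5.4 (Subject Responder) has two limbs, applied at Week 48 and at Week 96. A subject responds if he or she is "a subject whose ETDRS score of the treated eye is at least 15 letters better than the sham eye", or is one "whose treated eye has a LogMAR acuity of at least 0.3 LogMAR better than the sham eye". Both compare acuity levels at the visit.

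Three other places bear on this:

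- SAP 5.4, Eye Responder Definition 1, does use baseline in its first limb: "an improvement of at least 15 letters in the ETDRS score compared to baseline". The primary response (SAP 4.1 and 9.5.1) is also change from baseline.
- SAP 3.3 calls 15 letters or 0.3 LogMAR between the eyes at outcome a clinically reliable difference. The SD paired with that threshold, however, is for change: "the standard deviation (SD) for visual acuity of the between-eye difference in change from baseline was calculated as 0.594".
- SAP 9.5.5 (Subject responders) plans "a randomization test comparing the observed rate of responders to the expected rate of responders under" the null hypothesis, and then says: "Expected rate is defined as responder rate in the Sham group based on an improvement of at least 15 letters in the ETDRS score compared" with baseline, or acuity better than 20/200 Snellen.

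The plan expects the eyes to differ at entry. SAP 3.1 says that "the best- or worst-seeing eye at entry can be a confounding factor". Protocol 8.6 ranks the eyes before randomisation and provides for extreme asymmetry: "If one eye of a subject is able to read letters on the ETDRS chart and one eye cannot", the eye that can is ranked better. The selection criteria in Protocol 5.2.1 set a floor for each eye but no limit on the difference between them.

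**The concern.** Allocation is balanced so that GS010 goes to the better-seeing eye in about half of subjects and to the worse-seeing eye in the rest. About half therefore start with the treated eye ahead and half with it behind. A rule on the final gap adds that head start or handicap to whatever happened after injection.

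Two things are at stake. Individual subjects are labelled wrongly in both directions. The subject-level rate also depends on which eye was treated, even when the treatment does nothing. The second matters because a stated secondary objective (SAP 2) asks whether responder rates and the treatment effect depend on treating the best- or worst-seeing eye. A score with entry status built into it cannot answer that cleanly.

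**Working it through.** **The plan's own figure.** SAP 3.3 gives 84% power for a 0.3 LogMAR between-eye difference with SD 0.594 and 36 subjects. A two-sided paired t-test at 0.05 with d = 0.3/0.594 = 0.505 and noncentrality 0.505 × √36 = 3.03 gives 83.8%. The figure reproduces, so 0.594 is being used as the SD of the between-eye difference in change. No rate or power is stated for Subject Responder.

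**Worked cases.** These need no distributional assumption.

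- Treated eye 40 letters and sham eye 20 at baseline, both unchanged. The final gap is 40 − 20 = 20, so the subject is a responder, with a relative gain of 0.
- Treated worse-seeing eye 10 → 30 letters, sham eye 30 → 30. The relative gain is 20 letters and the final gap is 0, so the subject is a non-responder.
- In LogMAR: the treated eye starts 0.3 behind and gains 0.5 relative to sham. It ends 0.2 ahead, so the subject is a non-responder.

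**Size.** Let G be the treated-eye advantage at baseline and Δ the treated-eye relative gain, both in LogMAR with positive meaning better.

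- Rule as written: responder if G + Δ ≥ 0.3.
- Change rule: responder if Δ ≥ 0.3.
- Inputs: Δ ~ N(effect, 0.594), SD from SAP 3.3; G ~ N(0, s), assumed independent of Δ.
- The documents do not give s, so 0.2 / 0.4 / 0.6 is shown. As a rough plausibility check, take the planning letter SD of 28.3 and 0.02 LogMAR per letter. The gap SD is then 28.3 × √(2(1 − r)) × 0.02, which spans 0.2 to 0.6 for inter-eye correlations r of about 0.94 to 0.44.

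With no effect, the change rule gives 1 − Φ(0.3/0.594) = 31%. The rule as written gives 1 − Φ(0.3/√(s² + 0.594²)) overall. The other rows come from simulating the same model.

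| No effect | s = 0.2 | s = 0.4 | s = 0.6 |
|---|---|---|---|
| Responders, overall | 32% | 34% | 36% |
| Better eye treated | 41% | 51% | 59% |
| Worse eye treated | 22% | 17% | 13% |
| Responders with relative gain below 0.3 | 16% | 30% | 40% |
| Relative gainers (≥ 0.3) missed | 13% | 23% | 29% |
| Missed, among treated worse-seeing eyes | 27% | 46% | 58% |

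With a true effect of 0.3, both rules give 50% overall.

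**Does the planned test repair it?** No. Its expected rate is the proportion of sham eyes that improve by 15 letters or exceed 20/200. That is a different quantity from the chance that one eye leads its fellow by 15 letters. Correcting the expected rate alone would still leave subjects mislabelled.

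**The case against.** The strongest defence is that the level-based rule is deliberate. SAP 3.3 words its clinically reliable difference as one at outcome, and Subject Responder matches it. Absolute Week 48 LogMAR is also a listed sensitivity analysis, so the plan looks at levels elsewhere. This explains the drafting, and the definition is not a plain contradiction of SAP 3.3. It does not make an unchanged entry gap a response.

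The second objection concerns independence, and it stands. If instead the gap has the same SD at both visits, the baseline and Week 48 gaps correlate at 1 − 0.594²/(2s²), and regression to the mean enters. With no effect, the rates for better / worse eye treated are then:

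- s = 0.4: 20% / 25% for the rule as written, 8% / 53% for the change rule.
- s = 0.6: 46% / 16% for the rule as written, 16% / 45% for the change rule.

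So a change rule is not guaranteed to be free of dependence on the eye treated.

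A reader might also infer that the rule **loses power**. The documents do not support that. For an exact test of treated-better against sham-better subjects, with a 0.3 effect and n = 36, power on levels under independence is 63 / 51 / 38% (s = 0.2 / 0.4 / 0.6), against about 66–69% on change. Under equal gap SDs it is 96% against 68% at s = 0.4 (which needs a negative correlation), 83% against 68% at 0.5, 66% against 68% at 0.6, and 40% against 68% at 0.8. The direction turns on a correlation the documents do not give, and the SAP does not plan this test.

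A reader might further infer a **bias toward GS010**. Randomisation of the treated eye, balanced over better- and worse-seeing eyes, makes the errors roughly symmetric. The overall null rate moves only from 31% to 32–36%, and not at all under a 0.3 effect.

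Finally, the endpoint is supportive (SAP 9.5.3) and does not appear in the protocol. The primary analyses use change with baseline LogMAR as a covariate and are unaffected.

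**Conclusion.** The point holds as a defect in the definition of a supportive endpoint. As written, an unchanged entry gap of 15 letters or 0.3 LogMAR in the treated eye's favour is a response, and a real relative gain in a treated worse-seeing eye can be scored as none. That follows from the text alone, and no other section repairs it.

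The size is illustrative. With no effect, and a baseline gap independent of change with SD 0.2 to 0.6 LogMAR, 16–40% of responders have no 0.3 relative gain and 13–29% of relative gainers are missed. The percentages depend on both assumptions. The consequence is misclassification and a rate that cannot be read as a response rate. No one-directional bias, power loss or effect on the primary analysis is established.

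**What to change.** - In SAP 5.4, define Subject Responder at Weeks 48 and 96 as treated-eye change from baseline minus sham-eye change from baseline of −0.3 LogMAR or better, or at least 15 letters where both eyes have letter scores at both visits.
- In SAP 9.5.5, derive the expected rate under the null for that same definition by re-labelling treated and sham eyes within subject. This is essential: with SD 0.594, the change rule still labels about 31% of subjects responders when there is no effect.
- Report the rate separately by whether the best- or worst-seeing eye was treated.
- Keep the raw between-eye gap at each visit as a descriptive line.

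The cost is one definition, one matching null-rate derivation and one extra table split, all from data already collected. The downside is that baseline measurement error and regression to the mean enter the score, which is why the split by eye treated is needed. Protocol Appendix V bars SAP amendments after the code is broken, so the change must precede the Week 48 unmasking; otherwise it would count as a post hoc analysis.
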